12.6.2 Vital Signs

Vital signs and change from baseline will be summarized descriptively at each visit by treatment group. Additionally the number of subjects with the following vital signs of special interest will be summarized descriptively by treatment group:

- Systolic BP levels ≥ 180 mmHg
- Diastolic BP levels ≥ 100 mmHg
- Heart rate ≥ 180 beats/min
- Heart rate ≤ 60 beats/min

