8.3.4. Vital Signs

Vital signs will be measured at the Day 270, 300, and 365/ET Visits. After resting in the seated position for 5 minutes, vital signs measured will include temperature, sitting blood pressure, heart rate, respiratory rate, and oxygen saturation on room air. The method of temperature measurement should be according to the Site's policy and should be consistently applied.

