8.4.5.2. AESIs Related to Other Medical Problems

Several medical problems are frequently observed in patients with diabetic peripheral neuropathy that should be considered AESIs. These medical problems are listed below by type of medical problem.

Infections and Infestations; Skin and Subcutaneous Disorders

Because patients with diabetic peripheral neuropathy are at an increased risk to develop skin lesions (e.g., blisters, ulcers) and various lower limb infectious complications (e.g., cellulitis, osteomyelitis) that may be associated with systemic infections (e.g., bacteremia, sepsis, or septic shock), all of these types of medical problems that occur between the Day 180 (VMDN-003-02) and the Day 365/ET (VMDN-003-2b) Visits will be considered AESIs. In addition, any amputations involving the lower extremity, development of Charcot foot, or other similar complications will also be considered AESIs.

Peripheral Arterial Disease

An overlap of DPN and peripheral artery disease (PAD) apparently exists in type 2 diabetic patients. ⁴⁶ Because Participants with DPN may develop signs or symptoms of PAD between the Day 180 (VMDN-003-2) and the Day 365/ET (VMDN-003-2b) Visits, detailed evaluations of Participants considered to have PAD will be considered AESIs.

Version 1.0 43 Final: 11 Feb 2021

Diabetic Neuropathies

Because Participants in this study may develop other types of diabetic peripheral neuropathies while in the study, the following events will be considered to be AESIs in Participants with DPN: diabetic mononeuropathy, diabetic mononeuropathy multiplex, and diabetic polyradiculopathy. The occurrence of these other types of peripheral neuropathies in a Participant with DPN may indicate a more severe form of DPN.

Because Participants in this study may develop various manifestations of autonomic neuropathy (typically involves the gastrointestinal, genitourinary tract, cardiovascular systems) after randomization, the clinical manifestations of diabetic autonomic neuropathy will be considered to be AESIs.

Glycemic Control

Hypoglycemia, hyperglycemia, hyperlipidemia, hypercholesterolemia, and hypertriglyceridemia are to be listed as AESIs based on the Common Terminology Criteria for Adverse Events (CTCAE) grading if they are Grades 3 or 4.

Metabolic complications of DM (such as diabetic ketoacidosis [DKA], hyperglycemic hyperosmolar non-ketotic coma, lactic acidosis, metabolic acidosis [overlaps with DKA]) are to be listed as AESIs.

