12.2 Demographic and Baseline Characteristics

The following outcomes will be summarized by the standard methods for continuous and categorical variables described in Section 8.1.

The demographics include the following parameters:

- Age at informed consent of main study
- Sex
- Race
- Ethnicity
- Vital signs: height, weight, BMI,

The baseline characteristics include the following:

- Baseline Average Daily Pain Score from the 7 days prior to the Day 0 Visit obtained from the BPI-DPN eDiary
- Vital signs: blood pressure, heart rate, respiration rate, temperature
- Diabetes type
- 12-lead electrocardiogram (ECG): Normal, Abnormal Not Clinically Significant (NCS), Abnormal Clinically Significant (CS)

These parameters will be summarized by treatment group for the ITT and included in data listings. The demographic and selected baseline characteristics (diabetes type and specific medical history items of interest) will also be summarized for each level of the stratification variable.

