12.6.5 Electrocardiogram (ECG)

The collected ECG values will be listed.

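### The SAP's high heart-rate count (180 beats/min or more) tells almost nothing about a seated resting measurement, and post-baseline ECGs get no by-arm summary, so moderately fast rates and ECG changes not reported as adverse events go untabulated

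*SAP*

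**What the plan says.** **Heart rate.** Protocol 8.3.4 sets the measurement condition: "After resting in the seated position for 5 minutes, vital signs measured will include temperature, sitting blood pressure, heart rate". It is taken at Days 270, 300 and 365/ET. SAP 12.6.2 first provides for ordinary summaries: "Vital signs and change from baseline will be summarized descriptively at each visit by treatment group". SAP 12.0 defines these for continuous variables as mean, SD, median, minimum, maximum, quartiles and n. SAP 12.6.2 then adds by-arm counts of participants with vital signs of special interest. The heart-rate rows are "Heart rate ≥ 180 beats/min" and "Heart rate ≤ 60 beats/min". Two rows above the first of these stands "Systolic BP levels ≥ 180 mmHg".

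**ECG.** Protocol 8.3.3 schedules 12-lead ECGs on Days 270 and 365/ET. The whole of SAP 12.6.5 is one sentence: "The collected ECG values will be listed". At baseline, SAP 12.2 summarises the ECG by treatment group in three categories: "12-lead electrocardiogram (ECG): Normal, Abnormal Not Clinically Significant (NCS), Abnormal Clinically Significant (CS").

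**Adverse event route.** Protocol 1.3, footnote 4, has any newly identified ECG abnormality recorded as an adverse event. Protocol 8.3.3 asks this only of clinically significant ones. SAP 12.6.1 tabulates treatment-emergent events by arm, by system organ class and preferred term.

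**The concern.** The SAP adds threshold counts to the continuous summaries because means and quartiles do not show how many individuals had unusual values. For fast heart rate, that count is set where a resting reading will almost never fall. Zero against zero could then be read as an absence of tachycardia in either arm, when the row had almost no capacity to find any. The low row has the opposite weakness, because 60 beats/min or less can include ordinary resting rates. Neither row separates participants who already met the cut-off at baseline.

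For ECG, the baseline table has no post-baseline counterpart. Laboratory values get by-arm shift tables (SAP 12.6.3) and fundoscopy changes are summarised by arm (SAP 12.6.4). Of SAP 12.6.1 to 12.6.6, only the ECG section has no by-arm summary.

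Cardiac safety has some weight here. Protocol 8.4.5.1 makes recent coronary artery disease an angiogenesis-related AESI. Protocol 2.3.1 reports a myocardial infarction that the sponsor categorised as possibly related. Protocol 8.4.5.2, which names the cardiovascular system among those typically involved, states that "the clinical manifestations of diabetic autonomic neuropathy will be considered to be AESIs". Long-term safety is one of the extension's stated purposes.

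**Working it through.** The documents give no sample size, expected event count or heart-rate distribution for this point, so there is no planned figure to reproduce. The distributions below are assumptions, used only for scale.

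**1. Can a resting reading reach 180?** Assume normal resting rates with mean m from 70 to 90 and SD s from 10 to 15 beats/min. Let z = (180 − m)/s.
- Farthest: (180 − 70)/10 = 11.0 SD.
- Nearest: (180 − 90)/15 = 6.0 SD, giving P(≥ 180) = 9.9 × 10⁻¹⁰ per reading.
- Even 1,000 readings at the nearest setting give 1,000 × 9.9 × 10⁻¹⁰ ≈ 10⁻⁶ expected.

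**2. What other cut-offs would catch, over the same range**

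| Cut-off (beats/min) | Lowest probability | Highest probability |
|---|---|---|
| 60 or less | 0.1% (m 90, s 10) | 25% (m 70, s 15) |
| 100 or more | 0.1% (m 70, s 10) | 25% (m 90, s 15) |
| 120 or more | 0.00003% (m 70, s 10) | 2.3% (m 90, s 15) |
| 180 or more | essentially 0 | 0.0000001% (m 90, s 15) |

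**3. A general shift.** Assume a control mean of 78, SD 12, 100 per arm, and a rise of 10 beats/min in one arm.
- At 100 or more: z = (100 − 78)/12 = 1.83 gives 3.3 expected; z = (100 − 88)/12 = 1.00 gives 15.9.
- At 180 or more: about 0 in each arm.
- The planned mean-change summary does carry this shift. A two-sided 5% comparison of means would have power of about 0.99 with 50 per arm (for a 5 beats/min shift, 0.55 with 50 and 0.84 with 100). The SAP plans no such test; the figures show only that the information is in the summary.

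**4. A rise in a minority.** Same control arm; in the other arm 5% rise by 40 beats/min, to a mean of 118 with SD 12.
- Mean: 0.05 × 40 = 2 beats/min higher.
- Upper quartile: from 78 + 0.674 × 12 = 86.1 to 87.6, where 87.6 solves 0.95 Φ((x − 78)/12) + 0.05 Φ((x − 118)/12) = 0.75.
- Count at 100 or more: 100 × (0.95 × 0.0334 + 0.05 × 0.933) = 7.8, against 3.3.
- Count at 180 or more: z = (180 − 118)/12 = 5.17, P = 1.2 × 10⁻⁷, so 100 × 0.05 × 1.2 × 10⁻⁷ = 6 × 10⁻⁷.

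The mean and upper quartile barely move, a reachable cut-off roughly doubles its count, and the 180 row stays empty. The maximum would probably rise, but it reflects one participant per visit.

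**5. ECG outlets, side by side**

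| Outlet | By arm after baseline? | What gets in |
|---|---|---|
| SAP 12.2 category table | No, baseline only | All participants |
| SAP 12.6.5 listing | No summary | All collected values |
| TEAE tables (SAP 12.6.1) | Yes | Only what is reported as an event |

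The last outlet depends on reporting decisions. Protocol 1.3 footnote 4 and 8.3.3 set different scopes. Protocol 10.2.1 also excludes abnormal safety assessments associated with the underlying disease, even clinically significant ones, unless judged more severe than expected. In a diabetic population some ECG changes could be left out on that ground.

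**The case against.** A reader might infer that the plan cannot show any arm difference in fast heart rate or new ECG abnormality. The documents do not support that. Heart rate and its change from baseline are summarised by arm and visit, including the upper quartile and maximum, so a general shift or an extreme value would be visible. ECG abnormalities recorded as adverse events reach the by-arm TEAE tables. Coronary disease and autonomic neuropathy are AESIs with their own tabulation (SAP 12.6.1), and none of these depends on a scheduled heart-rate count.

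A reader might also infer that 180 was copied from the systolic pressure row. That is possible but not established. SAP 12.6.3 also uses extreme flags, such as AST at 10 times the upper limit of normal or more, so an extreme cut-off may be deliberate.

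Three further cautions stand:
- Normal tails do not describe a paroxysmal arrhythmia, so the row is not certain to be empty; it is very unlikely to be informative.
- The documents do not confirm that the ECG category is entered in the database at Days 270 and 365. The protocol says that the trace and interpretation are stored with the participant's records.
- The last main-study injection is on Day 104, so Days 270 and 365 fall 270 − 104 = 166 and 365 − 104 = 261 days later, and no safety testing is planned.

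These points narrow the concern without removing it. The SAP itself adds counts to the descriptive summaries, and this count does not do that job. The adverse event route is filtered and inconsistently defined.

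**Conclusion.** The concern holds in a limited form. The count at 180 beats/min or more is practically uninformative for a seated resting measurement: essentially zero is expected in both arms across assumed means of 70 to 90 and SDs of 10 to 15. The 60-or-less row could take in anything from 0.1% to 25% of readings under the same assumptions. No by-arm ECG summary is planned after baseline. Two things therefore go untabulated by arm: the number of participants with a moderately fast rate, and ECG category changes not reported as adverse events.

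The text findings need no assumption. The probabilities rest wholly on the assumed distributions, but the conclusion about 180 is the same throughout the range. The effect is confined to descriptive safety reporting; the primary and secondary efficacy analyses are untouched.

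**What to change.** Make these changes before unblinding, while categories can still be set without sight of results by arm.

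1. **SAP 12.6.2.** Replace the 180 beats/min row with a reporting cut-off that a resting measurement can reach, for example 100 or more with a higher second category. Reconsider the low cut-off. Count separately participants who did not meet the cut-off at main-study baseline. These are reporting categories only; they set no rule for care, and the values are for the sponsor to confirm. If 180 is intended, state why.
2. **SAP 12.6.5.** Add a by-arm shift table of ECG category (Normal / Abnormal NCS / Abnormal CS) from main-study baseline to Day 270 and to Day 365, using the interpretation recorded at each visit. Keep the listing.
3. **Protocol 1.3 footnote 4 and 8.3.3.** Reconcile the two statements of which ECG abnormalities are recorded as adverse events, and state how the result fits with the underlying-disease exclusion in 10.2.1.

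The cost is SAP wording, two small tables, and a check that the CRF captures the ECG category after baseline. If it does not, the interpretation would have to be retrieved from participants' records, which is more work than programming alone.

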12.6.3 HbA1c, Serum Chemistry, and Hematology

Central laboratory results will be summarized using International System (SI) of units. The laboratory results will be summarized by treatment and visit. The parameters within each panel are outlined in section 8.3.5.1 of the trial protocol, and lab panels for hematology and serum chemistry will be included.

Shift tables (i.e., low, normal, high at baseline versus low, normal, high at follow-up in a 3-by-3 contingency table) will be provided to assess changes in laboratory values from baseline to follow-up result at each scheduled follow-up visit. The counts and percentage of participants with each of the 9 possible “shift” outcomes will be calculated by treatment group. Individual laboratory data from scheduled and unscheduled visits will be listed.

Additionally the number of subjects with the following lab parameters of special interest will be summarized descriptively by treatment group:

- Glucose levels: critically high > 320 mg/dL (logic: 2-hour PP level for patients >60 years old is 160 mg/dl)
- Triglyceride levels: critically high \geq 500 mg/dL
- LDL cholesterol levels: critically high \geq 189 mg/dL
- Potassium levels: critically high \geq 5.5 mmol/L
- Hemoglobin levels: critically low \leq 6 g/dL
critically high \geq 20 g/dL
- WBC counts: critically low \leq 1,500/uL ($1.5 \times 10^9 / L$)
critically high \geq 20,000/uL ($20.0 \times 10^9 / L$)
- Platelet count: critically low \leq 50,000/uL ($50.0 \times 10^9 / L$)
critically high \geq 400,000/uL ($400.0 \times 10^9 / L$)
- Creatinine level: critically high \geq 2 mg/dL
- AST: critically high \geq 10 x ULN (upper limit of normal reference range)
- ALT: critically high \geq 10 x ULN (upper limit of normal reference range)
- Total bilirubin: critically high \geq 3 mg/dL

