2. INTRODUCTION

Engensis is a novel gene therapy treatment being developed for prolonged treatment of patients with painful diabetic peripheral neuropathy (DPN). The active pharmaceutical ingredient of

Engensis is VM202 (donaperminogene seltoplasmid), a plasmid deoxyribonucleic acid (DNA) designed as a gene transfer method to simultaneously express two isoforms of human hepatocyte growth factor (HGF), HGF₇₂₈ and HGF₇₂₃, that are identical to wild-type human forms.

Hepatocyte growth factor is a potent angiogenic and vasculogenic growth factor stimulating the growth of endothelial cells and migration of vascular smooth muscle cells. As a multifunctional mesenchyme-derived cytokine, it has potent angiogenic and anti-apoptotic effects, including that of the lymphatic system. In addition, HGF upregulates the expression of vascular endothelial growth factor (VEGF) and other factors and demonstrates greater mitogenic activity than that of VEGF alone in human aortic endothelial cells in vitro. HGF is also important in the pathophysiology of insulin resistance as well as a neurotrophic factor promoting axonal growth and regeneration in diabetics in whom loss of microvasculature may accelerate neuronal loss (see the Investigator's Brochure [IB] for more detailed information).

Compared with alternate modes of delivery of exogenous HGF into the systemic circulation, which is impeded by rapid clearance by the liver, direct administration of the plasmid DNA in Engensis into target tissues is followed by expression of HGF in situ, which results in a lowered risk of genomic integration (particularly in skeletal muscle tissue) and apparent lack of immune responses (such as observed with viral vector delivery systems), making it an attractive option for local targeted delivery. In addition, Engensis contains biological agents (promoters and controllers of gene transcription), including the unique plasma vector pCK that makes the expression from skeletal muscle more efficient (see the IB for full description of additional activities identified for Engensis). Engensis is detectable and expresses HGF for up to 30 days after direct skeletal muscle injection.

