12.0 Statistical Methods

The primary analysis for this study will be performed and summarized after all randomized participants have had an opportunity to complete their 12-month follow-up visit.

The Safety Analysis will be based on the Safety population. The primary analyses of the efficacy endpoints will be based on the ITT population. Additional sensitivity analyses for the primary and secondary efficacy endpoints will be performed to further assess the effects of the treatment (Section 8.4.2 and 8.4.4).

The statistical analyses will be reported using summary tables, figures and listings. Continuous variables will be summarized with mean, standard deviation, median, minimum, maximum, 25th percentile, 75th percentile, and number of non-missing observations for each treatment group.

Categorical variables will be summarized by counts and by the percentage of participants in corresponding categories.

All inferential statistical analyses will be performed with a two-sided confidence level of 95% or a two-sided significance level of 0.05 unless otherwise noted.

All analyses and tabulations will be performed using SAS Version 9.4 or higher on a Server platform.

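### HbA1c is set against each participant's own baseline only in a low/normal/high shift table, which is insensitive if most start above range; a baseline-adjusted Day 365 difference should be added

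*SAP*

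**What the plan says.** SAP 12.6.3 plans four outputs for laboratory data.

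- Group summaries: "The laboratory results will be summarized by treatment and visit". Under SAP 12.0 this means: "Continuous variables will be summarized with mean, standard deviation, median, minimum, maximum, 25th percentile, 75th percentile", with the number of observations.
- Within-participant comparison: "Shift tables (i.e., low, normal, high at baseline versus low, normal, high at follow-up in a 3-by-3 contingency table) will be provided".
- Listings: "Individual laboratory data from scheduled and unscheduled visits will be listed".
- Counts beyond critical limits. Glucose has one row ("Glucose levels: critically high > 320 mg/dL"); HbA1c has none.

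The section just before it, SAP 12.6.2, treats vital signs differently: "Vital signs and change from baseline will be summarized descriptively at each visit by treatment group".

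Four other places bear on the point.

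- The protocol's Schedule of Activities measures HbA1c once in the extension, at Day 365/ET.
- SAP 10.2 takes baseline from the last visit on or before the start of dosing in the main study, while SAP 12.6 limits safety summaries to extension-study data.
- SAP 12.2 does not list HbA1c among the baseline characteristics.
- SAP 10.6.1 and 12.5.3 nevertheless use baseline HbA1c, for imputing pain scores and for a subgroup, so the value is available.

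**The concern.** A three-category table has one category for everything above the reference range. A participant who goes from 7.5% to 10% starts *high* and ends *high*, in the same cell as one whose value did not move. In a population with diabetes that cell may hold most participants.

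The arm means by visit do not fully make up for this. They compare Day 365 levels without using the baseline value, which is usually the strongest predictor of the follow-up value. The comparison is also made in participants who completed Day 180 and consented, so balance from the main-study randomisation is not assured. With HbA1c missing from the baseline table and safety summaries limited to extension data, a literal reading could leave one Day 365 mean per arm with no baseline mean beside it.

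The documents give reasons to look. Long-term safety is a stated purpose. The protocol's introduction says "HGF is also important in the pathophysiology of insulin resistance as well as a neurotrophic factor". Its Section 8.4.5.2 makes glycaemic events of special interest: "Hypoglycemia, hyperglycemia, hyperlipidemia, hypercholesterolemia, and hypertriglyceridemia are to be listed as AESIs", at Grade 3 or 4. Glycaemic control may also bear on neuropathic pain, so an arm difference in HbA1c would help in reading the primary endpoint.

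**Working it through.** The documents give no sample size, HbA1c distribution, reference range or glycaemic effect, so there is no figure of the plan's own to reproduce. What follows illustrates sensitivity. Tests serve only as a yardstick, because the SAP plans none for safety.

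**Assumed inputs (none from the documents).** Baseline HbA1c mean 7.5–8.0%, SD *s* 1.2–1.5, upper limit of normal 6.0–6.5%, baseline-to-follow-up correlation ρ 0.5–0.7, *n* = 50–75 per arm, and a rise of 0.5 points in one arm only. Values are taken as bivariate normal.

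**Step 1. Who starts high.** Share = Φ((mean − limit)/*s*).

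- Mean 7.5, *s* 1.5, limit 6.5: Φ(0.667) = 74.8%.
- Mean 8.0, *s* 1.2, limit 6.0: Φ(1.667) = 95.2%.

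Over a wider grid (means 7.0–8.0, SD 1.0–1.5, limits 5.7–6.5) the share runs from 63% to 99%.

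**Step 2. What the shift table shows** (ρ = 0.7; no rise vs 0.5-point rise).

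| Mean, SD, limit | high→high | normal→high | high→normal |
|---|---|---|---|
| 7.5, 1.5, 6.5 | 64.7% vs 69.9% | 10.0% vs 14.2% | 10.0% vs 4.9% |
| 7.5, 1.0, 6.0 | 89.5% vs 92.4% | 3.9% vs 5.4% | 3.9% vs 1.0% |

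The table responds in both off-diagonal cells, but weakly. (The second row has a smaller SD than the main range and is shown only for its cells.)

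**Step 3. The *high* margin at follow-up.** This is the most favourable simple reading of the table.

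- First case: 74.8% vs Φ(1.5/1.5) = 84.1%. The gap is about 9.4 points, or 7 of 75 participants.
- Second case: 95.2% vs Φ(2.5/1.2) = 98.1%. The gap is about 2.9 points, or 1.5 of 50.

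In simulation with Fisher's test the rise is detected about 1–24% of the time. Using the normal→high cell alone gives 0–8%.

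**Step 4. Means.** The standard error of the arm difference is:

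- raw Day 365 means: *s*√(2/*n*)
- plain change: the raw value × √(2(1 − ρ))
- baseline-adjusted: the raw value × √(1 − ρ²), a factor of 0.87 at ρ = 0.5 and 0.71 at ρ = 0.7

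Detection ≈ Φ(0.5/SE − 1.96).

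| *s*, *n* per arm, ρ | raw SE | raw | plain change | adjusted |
|---|---|---|---|---|
| 1.5, 50, 0.5 | 0.300 | 39% | 39% | 49% |
| 1.5, 50, 0.7 | 0.300 | 39% | 58% | 65% |
| 1.2, 75, 0.5 | 0.196 | 72% | 72% | 84% |
| 1.2, 75, 0.7 | 0.196 | 72% | 91% | 95% |

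For example, in the first row the adjusted SE is 0.300 × 0.866 = 0.260, and Φ(0.5/0.260 − 1.96) = Φ(−0.04) ≈ 0.49. Simulation over the same settings gives 37–74% for raw means and 47–96% for the adjusted difference. This agrees with the formula to within a few points.

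**Step 5. What drives the gain.** At ρ = 0.5 the plain-change factor is √(2 × 0.5) = 1, so plain change adds no precision over raw means. Adjustment gains at either correlation.

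**The case against.** A reader might infer that a treatment-related worsening of glycaemic control could not show up in the planned outputs. The documents do not support that. Arm means by visit are planned in the same section, so a difference in Day 365 level would be displayed. The shift table can show worsening through more normal-to-high and fewer high-to-normal moves. Counts of glucose above 320 mg/dL, listings, adverse event tables and Grade 3 or 4 glycaemic events of special interest also exist, and clinically significant laboratory values are a secondary safety endpoint. All of this stands. None of it, however, is a summarised comparison of a moderate HbA1c change with the participant's own baseline.

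A reader might also infer that the protocol points to a known glycaemic harm. It does not. The introduction gives no direction of effect, the risk table lists no glycaemic risk, and the glycaemic events are grouped with problems common in this population. The case for the analysis is ordinary long-term safety reporting and interpretation of the primary endpoint.

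It can be said that most participants starting *high* is unproven. That is right: no HbA1c distribution or eligibility limit is given in these documents, and the statement must be read as an assumption.

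Finally, parity with vital signs would call only for plain change, and a modelled interval goes further in a descriptive section. That is fair, but Step 5 shows why plain change alone may not help. An interval without a test is compatible with the rule against formal safety testing.

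**Conclusion.** The point holds as a loss of sensitivity and interpretability for HbA1c. The only summarised within-participant analysis is poorly suited to a population likely to be above range already, and the by-visit means leave the available baseline unused. On the assumed inputs, baseline adjustment raises detection of a 0.5-point rise from 37–74% to 47–96%, against 1–24% from the shift table's *high* margin. The sizes depend on assumed sample size, SD, correlation, reference limit and effect. The direction of the gain from adjustment does not, provided baseline and follow-up are appreciably correlated. The change is worth making because it costs almost nothing; it does not call the trial's safety reporting as a whole into question.

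The case is weaker for glucose, since samples are random and its change will be noisy. It is not made for lipids, where triglycerides and LDL cholesterol already have threshold rows.

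**What to change.** Add to SAP 12.6.3: *HbA1c change from main-study baseline to Day 365 will be summarised by treatment group, with the baseline-adjusted mean difference (Engensis − Placebo) and 95% CI, descriptively and without a hypothesis test.*

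State there, or in SAP 12.6, that main-study baseline values are used for this summary and for the shift tables. This reconciles the limit to extension data in 12.6 with the baseline definition in 10.2; the shift tables need that clarification in any case.

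The shift tables can stay. A descriptive change in glucose may be added with a note that samples are not necessarily fasting. Lipids need nothing further.

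Cost: one or two sentences, one extra table, and a modelled interval in an otherwise descriptive section. No new data, visits or staff are needed, since baseline HbA1c is already required by SAP 10.6.1 and 12.5.3.
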